1.3.2 Other Diseases in Which Rituximab Use Has Been Described

This IgG1 chimeric monoclonal antibody was originally developed and approved for the treatment of non-Hodgkin's lymphoma. In addition, rituximab has been used in the treatment of chronic lymphocytic leukemia [70] and Waldenström's macroglobulinemia [71-73]. Post-approval experience has been estimated to include more than 2,484,131 (Genentech, 2011) patient exposures. Although reactions frequently occur with the first infusion, most are Grade 1 toxicity and respond to slowing or temporarily interrupting the infusion. In general, the drug has proven to be well tolerated, and serious reactions are very rare [74]. The period of B cell depletion with standard regimens of rituximab frequently averages 4 to 7 months [75, 76]. A total of 8.4% of patients from the All Exposure RA population demonstrated a CD19 count < lower limit of normal for 2 years or more following their last rituximab exposure. 1.5% of these patients had CD19 counts below the lower limit of quantification for at least 2 years. These patients are generally representative of the RA population with long-standing disease, previous use of multiple DMARDs, and high use of oral corticosteroids. Of note is the proportion of patients with low peripheral B-cell counts at baseline, prior to rituximab treatment, which correlates with those patients whose counts showed prolonged B cell depletion. The clinical relevance of prolonged peripheral B-cell depletion beyond two years following rituximab treatment is unknown; no safety signal has been identified in the prolonged B cell monitoring trials. The pattern of peripheral B cell depletion and repletion in granulomatosis with polyangiitis (GPA) and microscopic polyangiitis (MPA) patients included in the RAVE study was similar to that previously observed in patients with RA [77]. Effects on total immunoglobulin (Ig) levels have been much less striking, and evidence of immunodeficiency related to hypogammaglobulinemia has been rare. While rituximab results in the near-complete depletion of circulating B cells, the exact mechanism(s) of this effect remains poorly understood. Proposed mechanisms include induction of apoptosis, cellular clearance by the reticuloendothelial system through bound antibodies, complement mediated cell lysis, and antibody-dependent cellular cytotoxicity (ADCC) via Fc γ -bearing effector cells. One of the Fc receptors that may be involved in anti-CD20 mediated ADCC is Fc gamma receptor 3A (Fc γ RIIIA), and *FCGR3A* polymorphisms have been shown to influence the response to rituximab [78, 79]. In studies of patients with lymphoma and SLE, homozygosity for the 158V allele predicted more complete depletion than homozygous 158F or heterozygous 158VF alleles.

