6.5.5 Quarterly Monitoring Visits

Subjects who complete the Week 48 visit or who reach endpoint early after receiving **any** study drug, but whose B cell numbers have not recovered, will be followed at least quarterly to monitor recovery. Quarterly monitoring visits (12 weeks \pm 14 days from the last visit) will consist of obtaining a B cell count (at both the central lab *and* at Stanford Human Immune Processing Center for the Stanford Human Immune Monitoring Center) and CBC (at the central lab), and will continue until recovery or for 2 years after initial treatment (whichever occurs first). Recovery is defined as the time point at which B cells recover to within 10% of baseline levels; if a baseline value is not available then recovery is defined as a B cell level of at least 90% of the lower limit of normal. During this monitoring period, AEs and SAEs will be assessed, providing the subject has not withdrawn consent, only to capture any infectious event \geq Grade 3 using the NCI-CTCAE. No additional study-related data will be collected.

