6.5.6 Early Endpoint Visit

Subjects who withdraw early from the Baseline to Week 48 portion of the study will be asked to complete an Early Endpoint Visit. All scheduled exams, procedures, and laboratory tests scheduled for Week 24 will be performed at this visit, unless the early withdrawal is after that time, in which case all scheduled exams, procedures, and laboratory tests scheduled for Week 48 will be performed. If prohibited medications or treatments as defined in Section 5.6, *Prohibited Medications and Treatments* are required for treatment of progressive PAH, the Early Endpoint Visit, including the repeat right heart catheterization if withdrawal occurs prior to 24 weeks, should occur prior to the change in medication or therapy.

If the subject received **any** study drug prior to early endpoint and his/her B cell numbers have not recovered, that subject requires quarterly monitoring as described in Section 6.5.5, *Quarterly Monitoring Visits*.

Data from subjects who initiate rituximab therapy, but do not complete all study visits, will still be included in the Intent-to-Treat (ITT) and safety analyses.

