7.3.2 Collection Period

Adverse events NCI-CTCAE grade 2 and above will be collected from the time the subject signs the informed consent until he/she initiates study intervention or until he/she is determined to be ineligible to receive study intervention, if the investigator determines that the adverse event is related to a study-mandated procedure, treatment, or change in treatment.

For all participants, adverse events NCI-CTCAE grade 2 and above will be collected from the time of initiation of study intervention (i.e., the administration of the first dose of study drug/study drug as defined in Section 6.5.3.1, *Visit 3 [Day 0]*) until he/she completes study participation or until 30 days after he/she prematurely withdraws (without withdrawing consent) or is withdrawn from the study.

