Clinical assessments and sample collection will occur regularly through Week 48 with telephone follow-up conducted intermittently. If a subject has not recovered B cells by Week 48, B cell studies will be conducted quarterly until recovery is documented or for 2 years after initial treatment (whichever occurs first). Recovery is defined as the time point at which B cells recover to within 10% of baseline levels; if a baseline value is not available then recovery is defined as a B cell level of at least 90% of the lower limit of normal. During this quarterly monitoring period of B cell recovery, AEs and SAEs will be assessed, providing the subject has not withdrawn consent, to capture any infectious event \geq Grade 3 using the National Cancer Institute—Common Terminology Criteria for Adverse Events (NCI-CTCAE). No additional study-related data will be collected.

The primary efficacy endpoint is the change in 6MWD from baseline to 24 weeks after treatment initiation. Hemodynamic measures will be assessed at baseline and Week 24, contributing to the understanding of the relationship between PVR and clinical endpoints. Time to clinical worsening will be assessed as a secondary outcome measure through Week 48, contributing to the understanding of the relationship between PVR and clinical endpoints. Initiation of new therapy due to disease worsening prior to Week 24 will prompt an endpoint visit and right heart catheterization prior to initiation of the new therapy. B cell recovery for all will be monitored by serial assessments of B cell counts as determined by flow cytometry.

The total duration of the study is anticipated to be approximately 8 years.

Study Population: Any individual 18 to 75 years of age, who has been diagnosed with SSc-PAH within the past 5 years (as defined by a clinical diagnosis of SSc with a mPAP \geq 25 mmHg), a NYHA Functional Class of II, III, or IV, a mean PVR of $>$ 3 Wood units, and who meets all entry criteria is eligible for randomization.

Primary Efficacy Endpoint: Change in exercise capacity, assessed by 6MWD, from baseline to 24 weeks after treatment initiation.

Title of the Protocol: A Randomized, Double-blind, Placebo-Controlled, Phase II Multicenter Trial of a Monoclonal Antibody to CD20 (Rituximab) for the Treatment of Systemic Sclerosis-Associated Pulmonary Arterial Hypertension (SSc-PAH)

Secondary Efficacy Endpoints:

Secondary efficacy endpoints include the following clinical endpoints:

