8.2. Adverse Events

All AEs will be classified by system organ class (SOC) and preferred term, according to a standardized thesaurus (Medical Dictionary for Regulatory Activities [MedDRA] version 13.1). The severity of AEs will be classified using the National Cancer Institute's (NCI's) Common Toxicity Criteria for Adverse Events (CTCAE) version. Each AE is entered on the electronic case report form (eCRF) once at the highest severity. As such, no additional data manipulation is needed to identify events.

Adverse events NCI-CTCAE grade 2 and above will be collected from the time the subject signs the informed consent until he/she initiates study intervention or until he/she is determined to be ineligible to receive study intervention, if the investigator determines that the adverse event is related to a study-mandated procedure, treatment, or change in treatment.

For all participants, adverse events NCI-CTCAE grade 2 and above will be collected from the time of initiation of study intervention (i.e., the administration of the first dose of study drug/study drug) until he/she completes study participation or until 30 days after he/she prematurely withdraws (without withdrawing consent) or is withdrawn from the study. During the quarterly monitoring period of the study, only NCI-CTCAE grade 3 and higher infections are collected on the adverse events CRF page. Grade 3 and higher infections that occur during the quarterly monitoring period will be listed separately and will not be included in data tabulations, unless otherwise specified.

Treatment-emergent AEs will be identified as those with an onset date on or after the first dose of study medication. If the start of the AE in relation to the start of study medication cannot be established (e.g., the start date for the AE is missing), then the AE will be considered treatment-emergent. All data tabulations will be of only treatment-emergent events unless otherwise specified; non-treatment-emergent AEs will be listed.

An overall summary table will be developed to report the number of events and the number and percentage of subjects having at least one event in the following categories:

- AEs
- AEs requiring 24-hour reporting to the sponsor
- AEs indicated as serious
- AEs that lead to study drug discontinuation
- AEs with an outcome of death
- AEs by relationship to a study drug
- AEs reported by maximum severity

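### SAP 8.2 leaves out of the AE, SAE and infection tables any Grade 3+ infection before Week 48 that occurs more than 30 days after early exit in a subject with unrecovered B cells, and SAP Section 11 does not declare it

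*SAP*

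**What the plan says.** SAP 8.2 sets the tabulation rule: "Grade 3 and higher infections that occur during the quarterly monitoring period will be listed separately and will not be included in data tabulations", followed by an allowance for anything specified elsewhere. It gives no date on which the quarterly period begins.

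The protocol gives two ways into that period. Protocol 6.5.5 covers "Subjects who complete the Week 48 visit or who reach endpoint early after receiving" any study drug, if B cells have not recovered. Protocol 6.5.6 says of the early leaver with unrecovered B cells "that subject requires quarterly monitoring as described in Section 6.5.5". Protocol 3.3.2.1 (items 2 and 3) applies this to subjects whose PAH therapy must change before Week 24, and Protocol 3.1.1 has the need for quarterly visits communicated after Visit 16 or after the Early Endpoint visit.

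Ordinary collection of Grade 2 and higher events runs "until he/she completes study participation or until 30 days after he/she prematurely withdraws" (Protocol 7.3.2; SAP 8.2 repeats it). In quarterly monitoring only Grade 3+ infections are captured.

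The protocol's safety endpoints (3.2.3) include every infection event and every Grade 3–5 event, with no limit by period. Protocol 8.3.1 plans rates and proportions for all AEs and SAEs reported. SAP 8.2 bases percentages on the safety population and rates on person-time of exposure, whose end it does not define. SAP Section 11, the list of departures from the protocol, does not mention the exclusion.

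**The concern.** Whether a serious infection enters the tables depends on how it was collected, not on when it happened after dosing. Two infections of the same grade on the same study day can be treated differently because one subject has left the main study.

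Infection is a named safety endpoint of a B-cell-depleting treatment. The protocol notes that "The period of B cell depletion with standard regimens of rituximab frequently averages 4 to 7 months", roughly 17 to 30 weeks, so a rituximab subject who exits in the first months is likely to be unrecovered and to fall under the rule. Some of these subjects will have left because their PAH progressed. At stake is the completeness of the absolute infection counts and percentages to Week 48: the subjects remain in the denominator while their known later infections are removed from the numerator.

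**Working it through.** **The rule traced through one case.** The plan states no figure for this point, so the check is first a matter of definitions. I take the 30-day clock to start at the Early Endpoint visit.

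1. A subject receives study drug and has an Early Endpoint visit at Week 8 with unrecovered B cells. Consent is not withdrawn.
2. Ordinary AE collection ends 30/7 = 4.3 weeks later, at about Week 12.3.
3. A Grade 4 pneumonia at Week 18 is captured only through quarterly monitoring (Protocol 3.3.2.1 item 3, 6.5.5, 7.3.5).
4. Under SAP 8.2 it goes to the listing and not to the AE, Grade 3–5 or infection tables. SAP 8.3.1 builds the SAE tables in the same manner, so it is missing there too.
5. The same event at Week 18 in a subject still on study is tabulated.
6. The Week 8 leaver still counts in the n (%) denominator. One omitted event in 30 subjects is 1/30 = 3.3 percentage points.

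**How much could be left out.** Inputs from the documents: 30 subjects per arm (SAP 1), 20% drop-out (Protocol 8.1), 48 weeks of main study, 30-day tail. Assumptions: 6 of 30 leave in each arm, all at the same week, all alive, consenting and unrecovered to Week 48. This is deliberately on the high side.

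Excluded person-weeks per arm = 6 × (48 − exit week − 30/7). Planned person-weeks per arm = 30 × 48 = 1440. Expected omitted infections = risk per 48 weeks × excluded person-weeks / 48.

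| Exit week | Excluded person-weeks | Share of 1440 | Omitted at 2% | at 10% | at 20% |
|---|---|---|---|---|---|
| 4 | 238 | 16.5% | 0.10 | 0.50 | 0.99 |
| 12 | 190 | 13.2% | 0.08 | 0.40 | 0.79 |
| 24 | 118 | 8.2% | 0.05 | 0.25 | 0.49 |
| 36 | 46 | 3.2% | 0.02 | 0.10 | 0.19 |

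The 2% is the serious-infection frequency for rituximab in the pooled RA studies (Protocol 1.4). No period is given there, so applying it per 48 weeks, and to Grade 3+ events, is an assumption. The 10% and 20% are assumptions without a source in the documents.

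Quarterly monitoring may also be read as starting at exit, so that the 30-day tail is excluded too. The shares then become 18.3%, 15.0%, 10.0% and 5.0%. The SAP does not settle this overlap.

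**Direction by arm.** Under the present rule, tabulated collection for an early leaver stops at exit plus 30 days whether the subject had rituximab or placebo. After that point infections are captured only in unrecovered subjects, who will be mainly in the rituximab arm. The existing tables therefore have like-for-like cut-offs in the two arms. It is the omitted events whose ascertainment is unequal.

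**The case against.** The strongest reply is that the SAP means the period after Week 48. Its synopsis says "If a subject has not recovered B cells by Week 48, B cell studies will be conducted quarterly until recovery is documented", and SAP 8.3.2 separates the main study up to Week 48 from later deaths, mentioning quarterly monitoring only for the latter. On that reading the fault is a missing start date. This is a fair account of intent, but it does not remove the problem: the protocol that the SAP implements starts the period at early exit, and a programmer following both documents would omit the events.

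The rule also ends with an escape clause: such infections "will be listed separately and will not be included in data tabulations, unless otherwise specified". That would answer the point if SAP 8.2 or 8.3 used it for the tables. Neither does.

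Other mitigations stand. Excluded infections have their own listing. Infections up to 30 days after withdrawal fall under ordinary AE collection. The DSMB receives at least a listing of all reported AEs and SAEs (Protocol 7.8.2). All safety comparisons are exploratory (Protocol 8.3.1).

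Three stronger readings are tempting, and the documents do not support them.

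- A reader might infer that these infections vanish from every safety output. They do not: they are listed, and deaths count in all-cause mortality at Weeks 48 and 104 (SAP 8.3.2).
- A reader might infer that the rule biases the comparison against placebo because the omitted events are mainly in the rituximab arm. But the tabulated cut-off is the same in both arms. Simply adding the omitted events would itself create unequal ascertainment.
- A reader might size the defect by all ordinary AE collection lost to drop-out. With 12 leavers and exits spread evenly over Weeks 2–24, the mean loss is 48 − 13 − 4.3 = 30.7 weeks each, or 369 subject-weeks, 13% of 60 × 48 = 2880. With exits over Weeks 2–48 it is 227 (8%). These are upper bounds on lost collection. Deaths, consent withdrawals and recovered subjects contribute nothing to the events this rule removes.

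**Conclusion.** The point holds as a gap in completeness. Read with Protocol 3.3.2.1, 6.5.5 and 6.5.6, SAP 8.2 omits from the AE, SAE and infection tabulations known Grade 3+ infections before Week 48, when they occur more than 30 days after early exit in consenting subjects with unrecovered B cells. This is an undeclared narrowing of Protocol 3.2.3 and 8.3.1.

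Absolute counts and n (%) are understated. Poisson rates are understated only if exposure time is not cut where the events are, which the SAP leaves open. The rule does not by itself bias the between-arm comparison.

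The likely size is small: 0.02 to 0.10 expected omitted infections per arm at 2% per 48 weeks, and 0.19 to 0.99 at 20%. This rests on 20% drop-out in each arm, a common exit week between 4 and 36, every leaver staying unrecovered to Week 48, and the assumed risks. It merits correction because it touches a named safety endpoint and costs little.

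**What to change.** Change the SAP only.

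1. In 8.2, limit the list-only rule to Grade 3+ infections with onset after Week 48, and state when quarterly monitoring starts for an early leaver and how it relates to the 30-day tail.
2. Tabulate by arm all Grade 3+ infections with onset from first dose to Week 48. Put those arising after exit plus 30 days in a separate labelled row, with person-time that matches the period of capture and a stated exposure end date.
3. Beside it, show the table cut at exit plus 30 days in both arms. Use this one for the Fisher and Poisson between-arm comparisons.
4. Add a footnote that early leavers with recovered B cells, mainly placebo, are not followed for infection after 30 days.
5. Record the change in SAP Section 11.

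The cost is a few sentences and one extra table. The downside is that the full tabulation has unequal ascertainment by arm, so it should be read for absolute counts and not for the treatment comparison. Following all early leavers for infection to Week 48 would remove that limit, but it needs a protocol amendment, IRB approval and new contact with withdrawn subjects. It is not required for this correction.

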7.4 Grading and Attribution of Adverse Events

7.4.1 Grading Criteria

The study site will grade the severity of adverse events experienced by the study subjects according to the criteria set forth in the National Cancer Institute's *Common Terminology Criteria for Adverse Events Version (CTCAE) 4.0*. This document (referred to herein as the NCI-CTCAE manual) provides a common language to describe levels of severity, to analyze and interpret data, and to articulate the clinical significance of all adverse events. The NCI-CTCAE has been reviewed by the Protocol Chair(s) and has been deemed appropriate for the subject population to be studied in this protocol.

Adverse events will be graded on a scale from 1 to 5 according to the following standards in the NCI-CTCAE manual:

Grade 1 = mild adverse event.

Grade 2 = moderate adverse event.

Grade 3 = severe and undesirable adverse event.

Grade 4 = life-threatening or disabling adverse event.

Grade 5 = death.

If NCI-CTCAE criteria are defined for grading an abnormal value or result from a clinical or laboratory evaluation (including, but not limited to, a radiograph, an ultrasound, or an electrocardiogram), then a treatment-emergent adverse event is defined as an increase in grade from Baseline (Day 0) or from the last post-baseline value that doesn't meet grading criteria. Changes in grade from screening to Baseline (Day 0) will also be recorded as adverse events but are not treatment-emergent. If a specific event or result from a given clinical or laboratory evaluation is not included in the NCI-CTCAE manual, then an abnormal result would be considered an adverse event if changes in therapy or monitoring are implemented.

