- All NCI-CTCAE Grade 3-5 AEs, which are defined as possibly, probably, or definitely related to rituximab
- All NCI-CTCAE Grade 3-5 adverse events

- All infection related AEs

In addition, AEs classified by MedDRA SOC and preferred term will be summarized for each treatment group and overall for each of the following:

- All AEs
- AEs by maximum severity
- AEs by relationship to study drug: relationship to study treatment will be categorized as either treatment related (possibly, probably, or definitely related to study medication) or unrelated
- All infection related AEs

Summary tables will present the total number of events as well as the number and percentage of subjects experiencing the events. If a subject experiences the same AE on multiple occasions, the event will be counted once for each occurrence when reporting the number of AEs. When reporting the number of subjects experiencing the events, a subject will only be counted once if they experience an event within the particular SOC or preferred term. Percentages will be based on the number of subjects in the safety population.

AEs classified by MedDRA system organ class and preferred term will be summarized for each treatment group and overall, and incidence rates for AEs classified by MedDRA SOC and preferred term will be provided for each treatment group and overall. The incidence rate for a SOC or preferred term will be defined as the number of AEs divided by the person-time of exposure aggregated in each treatment group, and an analysis based on a Poisson regression model will be conducted to compare the rate of each type of event in the treatment groups. The proportion of subjects in each study arm experiencing each type of AE will be compared using a Fisher's Exact test.

Separate data listings will be provided for the following subsets:

- Treatment-related AEs
- AEs leading to study drug discontinuation
- Grade 3-5 AEs which are defined as possibly, probably, or definitely related to rituximab
- All Grade 3-5 AEs
- Infections
- Grade 3 and higher infections that occurred during the quarterly monitoring period
- AEs occurring from informed consent and prior to treatment initiation

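### SAP 8.2 has no worsening rule for treatment-emergent AEs, so an AE recorded before dosing that worsens afterwards on the same record falls out of the AE tables

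*SAP*

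**What the plan says.** SAP 8.2 sets the rule by date: "Treatment-emergent AEs will be identified as those with an onset date on or after the first dose of study medication". An event whose timing relative to the first dose cannot be established is also counted as treatment-emergent. There is no provision for worsening.

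On data entry, the same section says "Each AE is entered on the electronic case report form (eCRF) once at the highest severity", and concludes that no further processing is needed to identify events. On output it says "All data tabulations will be of only treatment-emergent events unless otherwise specified; non-treatment-emergent AEs will be listed". One of the separate listings is for "AEs occurring from informed consent and prior to treatment initiation".

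Protocol 7.4.1 approaches the matter through grade. Its condition is "If NCI-CTCAE criteria are defined for grading an abnormal value or result from a clinical or laboratory evaluation", and the consequence is "then a treatment-emergent adverse event is defined as an increase in grade from Baseline (Day 0) or from the last post-baseline value", the latter being a value that did not meet grading criteria. It adds that grade changes between screening and Day 0 are recorded as AEs but do not count as treatment-emergent.

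Protocol 7.3.2, repeated in SAP 8.2, limits other pre-dose collection to events of Grade 2 or above, and only "if the investigator determines that the adverse event is related to a study-mandated procedure, treatment, or change in treatment".

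**The concern.** The protocol deliberately creates some pre-dose AE records and separates them from what happens to the same finding after dosing. The SAP has only the start date to make that separation. With one record per event carrying the worst grade, a finding that was moderate before the infusion and severe after it appears as a severe event with a pre-dose start. It then goes to the listing of pre-treatment events, where it looks as if the severe grade had nothing to do with study drug.

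Worsening of an existing problem is a harm this protocol expects. Sections 1.4 and 5.3 both warn that the infusion may deepen low blood pressure already present at baseline. Grade 3-5 AEs are a safety endpoint in Protocol 3.2.3, and Protocol 8.3.1 does not restrict its between-arm AE comparisons to new-onset events.

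**Working it through.** No calculation in the plan bears on this, so the check is a comparison of rules.

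**1. Which records can have a pre-dose onset?** Two kinds: Grade 2 or higher events attributed to a study-mandated procedure, treatment or change in treatment (Protocol 7.3.2), and grade changes from screening to Day 0 (Protocol 7.4.1). Both arise only in the screening window of at most 28 days. A pre-existing condition never recorded as an AE is not among them; if it worsens after dosing it can enter as a new AE with a post-dose start.

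**2. What happens when such a finding worsens after dosing?** Take a gradable result that rises a grade between screening and Day 0, and rises again after the infusion.

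| | Protocol 7.4.1 | SAP 8.2, one record | SAP 8.2, two records |
|---|---|---|---|
| Rise before Day 0 | AE, not treatment-emergent | pre-dose onset | listed only |
| Rise after Day 0 | treatment-emergent | same record, now at the higher grade, still pre-dose onset: listed only | second record has post-dose onset: tabulated |

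The SAP and the protocol agree if sites open a second record, and disagree if they do not. Neither document states which is required. Entry once at the highest severity points to one record. So does Protocol 7.3.4, under which a recorded AE is followed until it resolves or the subject's follow-up ends.

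**3. Which outputs are affected?** The AE overview, the tables by system organ class and preferred term, and the tables by severity and relationship. The SAE tables in SAP 8.3.1 are to follow the same method, so they probably inherit the rule; the cross-reference there is to Section 8.3, where 8.2 seems to be meant.

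**4. Which outputs are not affected?** The AE listings in SAP 8.2; all-cause mortality from randomization (SAP 8.3.2); laboratory values, changes from baseline and abnormalities (SAP 8.4); vital signs (SAP 8.5.1).

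**5. A case that can arise.** Under Protocol 5.3 a subject with low pressure on Day 0 may be given fluid and still be infused. If that pressure is a grade rise from screening, 7.4.1 makes it a pre-dose AE. If the record is kept open and the pressure falls further during the infusion, the SAP leaves the event out of its AE tables.

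**6. Size.** Neither document gives a count of pre-dose AEs or of how many worsen. One subject in an arm of 30 is 1/30 = 3.3 percentage points, and only if that subject has no other event in the same table row. As an illustration on assumed rates only: if 5% to 15% of 60 subjects have a pre-dose AE and 20% of those worsen, then 60 × 0.05 × 0.20 = 0.6 to 60 × 0.15 × 0.20 = 1.8 subjects are affected, both arms together.

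**The case against.** The strongest reply is that 7.4.1 already describes two events. It defines the treatment-emergent AE as the increase itself, so the increase would have its own record and a post-dose start, and the SAP's date rule would catch it. SAP 8.2 also allows the same AE to occur more than once in a subject. This reading is possible, and it is why the loss is conditional. But it is stated nowhere, and it sits poorly with a single entry at the highest severity.

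A reader might infer that such events vanish from every safety table. They do not: they are listed, and the laboratory, vital-sign and mortality summaries do not depend on AE onset. Those summaries do not, however, replace tables by grade, relationship and organ class.

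A reader might also infer that worsening cytopenias, liver abnormalities or infections are the main casualties. The protocol's entry and infusion criteria make that unlikely. For example, Protocol 5.3.6 withholds infusion when ANC is below 1500/mm³, and Section 4.2 excludes raised transaminases or bilirubin at screening and recent infection needing antibiotics.

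Nor is the SAP rule contrary to the protocol for all AEs. The 7.4.1 definition covers gradable clinical or laboratory results; for other signs and symptoms the protocol defines no treatment-emergent rule.

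Finally, safety comparisons are exploratory (Protocol 8.3.1), only major changes must be noted (Protocol 8.5.6), and a figure in SAP Section 11 could not be read. These points lower the weight of the missing declaration but do not supply a worsening rule.

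**Conclusion.** The gap is real and narrow. As written, SAP 8.2 would leave out of the AE tabulations, and probably the SAE tables, any AE recorded before dosing that worsens afterwards and stays on one record. For gradable clinical or laboratory results this departs from Protocol 7.4.1, and none of the three readable entries in SAP Section 11 mentions it. The conclusion assumes that worsening updates the existing record; if sites open a new one, nothing is lost. The number affected cannot be derived and is probably small. The reason to act is that the rule errs towards omission in a trial with 30 subjects per arm, whereas the SAP's own handling of unknown start dates errs towards inclusion.

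**What to change.** Amend SAP 8.2 so that treatment-emergent AEs are those with onset on or after the first dose, or present before the first dose with an increase in grade on or after it, tabulated at the higher grade. Say that the same rule governs the SAE tables, and correct the cross-reference in SAP 8.3.1.

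State how the worsening is dated: from a separate AE record, from a query on the few pre-dose records, or from the laboratory and vital-sign data already collected. Do this before treatment assignments are unmasked. If the date-only rule is kept instead, declare the departure from Protocol 7.4.1 in SAP Section 11.

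The cost is a sentence or two of SAP text and a few data queries. No new assessments are needed.
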